8.4.10.2 Regulatory Reporting of SAEs

Following notification from the site Principal Investigator or appropriate sub-investigator, DMID, as the IND sponsor, will report any suspected unexpected serious adverse event (SUSAR) as an IND safety report to the FDA and will notify all participating site Principal

Investigators (i.e., all Principal Investigators to whom the sponsor is providing drug under its IND(s) or under any Principal Investigator's IND(s)) of potential serious risks from clinical studies or any other source, as soon as possible. DMID will report to the FDA any unexpected fatal or life-threatening suspected adverse reaction as soon as possible, but in no case later than 7 calendar days after the sponsor's initial receipt of the information. If the event is not fatal or life-threatening, the IND safety report will be submitted within 15 calendar days after the sponsor determines that the information qualifies for reporting as specified in 21 CFR Part 312.32. Relevant follow up information to an IND safety report will be submitted as soon as the information is available. Upon request from FDA, DMID will submit to the FDA any additional data or information that the agency deems necessary, as soon as possible, but in no case later than 15 calendar days after receiving the request.

SAEs that are not SUSARs will be reported to the FDA at least annually in a summary format which includes all SAEs.

8.4.11 Reporting Events to Participants

Not applicable

8.4.12 Adverse Events of Special Interest

Early clinical data indicates Sing2016 M2SR H3N2 vaccine is well tolerated in study participants. However, we will collect information about one AESI: wheezing. This AESI will be collected from the time of each study vaccination until the last visit for each individual participant. Details about wheezing and uniform collection of data are found in [Appendix B – Evaluation Criteria for Acute Wheezing](#).

All AESIs will be assessed, recorded, and followed as described above under adverse events. In addition, AESIs will be reported on an SAE form to the DMID Pharmacovigilance Group, at the following address:

DMID Pharmacovigilance Group
Clinical Research Operations and Management Support (CROMS)
[name]
[name]
SAE Hot Line: [name] (US) or [name] (outside US)
SAE [contact] (US) or [name] (outside US)
SAE Email Address: [contact]

8.4.13 Reporting of Pregnancy

All pregnancies that occur among study participants while enrolled in the study will be reported. If a female becomes pregnant before receiving study product, no product will be given, and her participation will end. Since the only cohort that includes females of childbearing potential is Cohort 1, and participants in this cohort are scheduled to receive a single dose of study product, it is not expected that a female scheduled for 2 doses of study product will become pregnant after one dose. For a female who becomes pregnant, we will request permission to continue to follow her, per protocol, for tolerability, safety, and immunogenicity. She may decline any or all subsequent study follow-up. We will also request to follow her pregnancy and record the outcome. This follow-up will include pregnancy outcome (termination, pre-term birth, term

birth) and newborn outcome (live birth, fetal demise, stillbirth; presence of any congenital anomalies). No in-person visits will be required for pregnancy outcome determination.

8.5 Unanticipated Problems

8.5.1 Definition of Unanticipated Problems (UP)

The Department of Health and Human Services Office for Human Research Protections (OHRP) considers unanticipated problems involving risks to participants or others to include, in general, any incident, experience, or outcome that meets all the following criteria:

- Unexpected in terms of nature, severity, or frequency given (a) the research procedures that are described in the protocol-related documents, such as the Institutional Review Board (IRB)-approved research protocol and informed consent document; and (b) the characteristics of the participant population being studied;
- Related or possibly related to participation in the research (“possibly related” means there is a reasonable possibility that the incident, experience, or outcome may have been caused by the procedures involved in the research); and
- Suggests that the research places participants or others at a greater risk of harm (including physical, psychological, economic, or social harm) than was previously known or recognized.

8.5.2 Unanticipated Problem Reporting

The investigator will report unanticipated problems (UPs) to the reviewing Institutional Review Board (IRB) and to the Statistical and Data Management Coordinating Center (SDMCC)/study sponsor and the lead principal investigator (PI). The UP report will include the following information:

- Protocol identifying information: protocol title and number, PI’s name, and the IRB project number;
- A detailed description of the event, incident, experience, or outcome;
- An explanation of the basis for determining that the event, incident, experience, or outcome represents an UP;
- A description of any changes to the protocol or other corrective actions that have been taken or are proposed in response to the UP.

To satisfy the requirement for prompt reporting, UPs will be reported using the following timeline:

- UPs that are serious adverse events (SAEs) will be reported to the IRB and as per [Section 8.4.7](#) Serious Adverse Event Reporting within 24 hours of the investigator becoming aware of the event.
- Any other UP will be reported to the IRB as per IRB guidelines and to the DCC/study sponsor within three days of the investigator becoming aware of the problem.

8.5.3 Reporting Unanticipated Problems to Participants

Not applicable

9. STATISTICAL CONSIDERATIONS

9.1 Statistical Hypotheses

This study is not designed to achieve pre-determined levels of power or precision to address the primary, secondary, or exploratory objectives. The power and precision allowed by the study's sample size are discussed in [Section 9.2](#), and the general methodology planned to address study objectives is described in [Section 9.4](#). Specific statistical hypotheses and details about planned tables, figures, and data listings will be presented in a separate statistical analysis plan.

9.2 Sample Size Considerations

[Table 5](#) gives the probability of observing one or more safety events, such as a reactogenicity event or an adverse event of a particular classification, for varying sample sizes, given underlying true event probabilities.

Table 5: Probability (%) of observing at least one safety event, given varying underlying event probabilities and sample sizes

Group	Group Size	Underlying Event Probability			
		0.01% (Very Rare)	0.1% (Rare)	1% (Uncommon)	10% (Common)
Cohorts 5-6 lead-in safety review, Cohorts 6-7 placebo	N=8	0.08	0.797	7.73	57
Cohort 3-4 placebo	N=10	0.1	1	9.6	65.1
Individual placebo group or Cohort 3-4 vaccine group	N=15	0.15	1.5	14	79.4
Individual vaccine group in Cohorts 6-7	N=18	0.18	1.78	16.5	85
Cohorts 1-2 safety review	N=25	0.25	2.5	22.2	92.8
Individual vaccine group in Cohorts 1-2;	N=30	0.3	3	26	95.8

Cohorts 3-4 aggregate vaccine groups, post first-dose					
Any Sing2016 M2SR H3N2 Vaccine, Cohorts 1-4	N=90	0.9	8.6	59.5	>99.9
Any Sing2016 M2SR H3N2 Vaccine	N=132	1.31	12.4	73.5	>99.9

Among the 25 participants in each of Cohorts 1-2 considered for the safety reviews prior to enrolling the subsequent cohorts, there will be a 22.2% chance of observing at least one uncommon event and a 92.8% chance of observing at least one common event (bolded and underlined in [Table 5](#)).

The primary objective of this study is to determine the safety and tolerability of the Sing2016 M2SR H3N2 influenza vaccine, which will be assessed via the incidence of adverse events of different types. While the study was not designed to achieve a pre-determined level of precision, confidence intervals will be estimated for some of the binary endpoints. [Table 6](#) presents the exact 95% Clopper-Pearson confidence intervals that would result from observing varying numbers of events in groups of possible interest.

Table 6: Estimated event probabilities (%) and associated exact 95% Clopper-Pearson confidence intervals resulting from varying numbers of events observed in groups of different sizes.

Group Size	Number of Events Observed								
	0	4	5	7	9	12	15	45	66
Cohorts 5-6 lead-in safety review, Cohorts 6-7 placebo (N=8)	0 (0, 36.9)	50 (15.7, 84.3)	62.5 (24.5, 91.5)	87.5 (47.3, 99.7)	-	-	-	-	-
Cohort 3-4 placebo (N=10)	0 (0, 30.8)	40 (12.2, 73.8)	50 (18.7, 81.3)	70 (34.8, 93.3)	90 (55.5, 99.7)	-	-	-	-
Individual placebo group or Cohort 3-4 vaccine group (N=15)	0 (0, 21.8)	26.7 (7.8, 55.1)	33.3 (11.8, 61.6)	46.7 (21.3, 73.4)	60 (32.3, 83.7)	80 (51.9, 95.7)	100 (78.2, 100)	-	-
Individual vaccine group in Cohorts 6-7 (N=18)	0 (0, 18.5)	22.2 (6.4, 47.6)	27.8 (9.7, 53.5)	38.9 (17.3, 64.3)	50 (26, 74)	66.7 (41, 86.7)	83.3 (58.6, 96.4)	-	-
Cohorts 1-2safety review (N=25)	0 (0, 13.7)	16 (4.5, 36.1)	20 (6.8, 40.7)	28 (12.1, 49.4)	36 (18, 57.5)	48 (27.8, 68.7)	60 (38.7, 78.9)	-	-
Individual vaccine group in Cohorts 1-2; Cohorts 3-4 aggregate vaccine groups, post first-dose (N=30)	0 (0, 11.6)	13.3 (3.8, 30.7)	16.7 (5.6, 34.7)	23.3 (9.9, 42.3)	30 (14.7, 49.4)	40 (22.7, 59.4)	50 (31.3, 68.7)	-	-
Any Sing2016 M2SR H3N2 Vaccine, Cohorts 1-4 (N=90)	0 (0, 4)	4.4 (1.2, 11)	5.6 (1.8, 12.5)	7.8 (3.2, 15.4)	10 (4.7, 18.1)	13.3 (7.1, 22.1)	16.7 (9.6, 26)	50 (39.3, 60.7)	73.3 (63, 82.1)

Any									
Sing2016	0								
M2SR H3N2	(0,	3.0	3.8	5.3	6.8	9.1	11.4		50.0
Vaccine	2.8	(0.8,	(1.2,	(2.2,	(3.2,	(4.8,	(6.5,		(41.2,
(N=132))	7.6)	8.6)	10.6)	12.5)	15.3)	18)	-	58.8)

For illustration, if zero events of a certain type were observed in an individual vaccine group or in Cohorts 3-4 aggregate vaccine groups after one dose with N=30 participants, true event probabilities above 11.6% could be ruled out at the $\alpha=0.025$ level, compared to 2.8% in the combined vaccine groups (N=132). Binomial confidence intervals are widest at 50% events observed; the estimates associated with approximately (or exactly) 50% observed events are bolded in [Table 6](#). Within an individual vaccine group or in Cohorts 3-4 aggregate vaccine groups after one dose with N=30 participants, the maximum half-width for a 95% CI would be 18.7%, compared to 10.7% across active vaccine groups in Cohorts 1-4. In the case of substantial loss to follow-up or missed visits, these estimates give an idea of the loss of precision due to decreasing the effective sample size.

While no formal hypothesis testing is planned for this study, some limited statistical testing may be conducted to aid interpretation of the strength of the results. Comparisons would be primarily focused on vaccine to placebo within a given cohort, due to the likelihood of confounding in most results due to age, dose level, or the number of doses (see [Section 9.4.1](#) for details on analysis groupings).

[Table 7](#) presents the probability of a binary event of interest (e.g., adverse event, reactogenicity, seroconversion, etc.) in a vaccine group of size N=30 (Cohorts 1 or 2) that would be detectable with 80% or 90% power given varying event probabilities in a placebo group of size N=15, using two-sided Barnard's exact tests at the $\alpha=0.05$ -level.

Table 7: Detectable probabilities (%) with 80% or 90% power when comparing binary event probabilities between groups with two-sided Barnard's exact tests with $\alpha=0.05$.

Probability in Placebo Group (N=15)	Detectable Probability in Vaccine Group (N=30)	
	80% power	90% power
0.1% (Rare)	29.0	32.9
1% (Uncommon)	31.5	36.5
10% (Common)	48.4	54.4
50% (Very Common)	88.2	92.4

There would be 80% power to detect a difference of 29% between vaccine and placebo groups for a rare event (0.1% probability) in the placebo group, compared to a difference of at least 48% for a common or very common event in the placebo group.

9.3 Populations for Analyses

- The enrolled population will include all participants enrolled and randomized

- The Safety population will include all participants who receive at least one study influenza vaccination.
- The Modified Intent-to-Treat (mITT) population will consist of all participants who received study influenza vaccination and reported baseline and at least one post-baseline immunogenicity result.
- The Per-Protocol (PP) population will include participants in the mITT population with the following exclusions of data:
 - Data from participants determined to be ineligible at baseline (determined thereafter)
 - Data from participants in Cohorts 4, 5, 6, and 7 subsequent to missed second study vaccinations
 - Data from any visit that occurs substantially out of window as defined in the SAP
 - Data from all visits subsequent to major protocol deviations, as defined in the SAP, that could impact the validity of later data, such as:
 - Receipt of immunosuppression or any medications that may be associated with impaired responsiveness
 - Receipt of any non-study investigational drug/investigational vaccine/licensed vaccine

The enrolled population will be used for summaries of participant disposition as well as participant demographics and baseline characteristics. The Safety population will be used for all analyses of adverse events and reactogenicity. Immunogenicity analyses will be done in the mITT population, and if sufficient data (>10% of secondary analysis observations) would be excluded by the PP exclusions, the PP population will be used for sensitivity analyses. Certain analyses may be done on subsets of these populations, such as by-dose analysis, where applicable, and these would be specified in the analysis plan.

9.4 Statistical Analyses

The primary clinical database for this study will consist of safety (adverse events and reactogenicity) and baseline/demographic data. Once the last participant has completed the final visit, the primary clinical database will be cleaned, monitored, and locked. After clinical database lock and receipt of secondary immunogenicity data, a set of topline tables will be generated by the Statistical and Data Management Coordinating Center (SDMCC), including summaries of clinical safety and secondary immunogenicity data. The topline report will be made available to the study team for planning subsequent trials and may be presented in a public forum or used for publication in collaboration with lead PI. These analyses will be considered final and will be included in the Clinical Study Report (CSR) as well. The CSR, comprised of the final analyses of safety and available immunological data, will be subsequently completed. Any available data from the exploratory endpoints may also be included. Additional exploratory endpoint data not available at the time of CSR preparation may be included in one or more addenda to the CSR, manuscript(s), or other report. A formal Statistical Analysis Plan (SAP) that specifies all planned analyses will be finalized prior to generating the topline report and CSR.

In addition to the descriptive analyses of study data for SRC and SMC review, an interim analysis is planned for while the study is ongoing to allow for an early assessment of the humoral immunogenicity of the study vaccine and to aid in decision-making regarding future studies. These analyses would not affect the conduct of this trial via early stopping, and participant-level unblinding will not occur until the clinical database is locked. Additional details on interim analyses are given in [Section 9.4.6](#).

The formal SAP will elaborate on the analyses described here.

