6.3.3 Blinding and Masking Procedures

This is a double-blind (masked) clinical trial. Participants, site investigators, and study personnel performing any study-related assessments following study product administration are blinded to product received. Laboratory personnel performing immunological assays will receive serum blinded to participant ID number, specimen visit number, and allocation group.

The randomization scheme will be generated by the SDMCC and provided to unblinded study personnel (i.e., research pharmacists performing study vaccination preparations and unblinded study vaccine administrators) at the participating CIVIC sites.

The unblinded or blinded study vaccine administrator is a study personnel member credentialed to administer vaccines. The unblinded vaccinator may also participate in dose preparation but will not be involved in study-related assessments or have participant contact for data collection following study vaccine administration. When participants receive IIV4, it is not necessary that vaccine is given by an unblinded member of the study team.

The SRC and the SMC will receive data in aggregate and the SMC may be presented data by aliased treatment group. The actual treatment assignments will be provided to the SMC at their request, but the SRC, as part of their review, will remain blinded. The SMC may also be provided with expected and observed rates of the expected AEs in an unblinded fashion and may request the treatment assignment be unblinded for an individual participant if required for safety assessment. The SMC will review grouped and unblinded data in the closed session only.

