4.5.5. Blinding

An unblinded interim immunogenicity analysis was performed (further details can be found in [Section 5.6.1](#)). These analyses were made available to the pharmaceutical partner for planning for future studies, with no public dissemination of results, and not used to make any decisions concerning the conduct of the trial. The SAP was finalized prior to unblinding of individual participants for the pharmaceutical partner and PI.

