4.6.2. Immunogenicity Variables

Hemagglutination inhibition (HAI) and microneutralization (MN) antibody results as measured in serum will be reported by the research laboratory at Duke University. HAI, MN antibody titers and neuraminidase inhibition (NAI) titers as measured in plasma will be reported by the laboratory at VisMederi. Assay results for HAI and MN, as measured in serum and plasma, and NAI as measured in plasma, are reported as endpoint titers, with values of 10^*2^k , where $k=0, 1, 2, \text{ etc.}$, or are reported to be below the lower limit of detection (LOD). Antigen specific non-dilution adjusted ECL signals, dilution factors, and total sIgA concentrations, as measured by BAMA, will be reported by the research laboratory at Duke University. sIgA titers and total sIgA concentrations, as measured by ELISA, will be reported by the laboratory at FluGen, Inc. See [Section 3.3](#) for definitions of derived variables for immunologic data.

All immunogenicity data will be uploaded into the SDMCC's electronic data capture system. Data for the remaining exploratory assays and corresponding analyses not covered in this document will be described in a separate analysis plan addendum(a).

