5.2. Timing of Analyses

The interim analysis was performed after all participants completed through 28 days post-first vaccination.

After clinical database lock and receipt of secondary immunogenicity data, a set of topline tables will be generated by the Statistical and Data Management Coordinating Center (SDMCC), including summaries of clinical safety and secondary immunogenicity data. These analyses will be considered final and will be included in the Clinical Study Report (CSR) as well. The CSR, comprised of the final analyses of safety and available immunological data, will be subsequently completed. Any available data from the exploratory endpoints may also be included. Additional exploratory endpoint data not available at the time of CSR

preparation may be included in one or more addenda to the CSR, manuscript(s), or other report. Plans for remaining analyses will be included in an addendum to the SAP with results presented in an addendum to the CSR after those data are available.

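### Individual treatment codes may be opened after clinical lock and SAP finalization, with no assay data frozen first; the exposure is late assays, above all the manufacturer's nasal sIgA ELISA

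*Protocol*

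**What the plan says.** On the timing of unblinding, Protocol 9.4 states that "participant-level unblinding will not occur until the clinical database is locked". The same section defines what is locked: "The primary clinical database for this study will consist of safety (adverse events and reactogenicity) and baseline/demographic data". Assay data enter at a separate step: "After clinical database lock and receipt of secondary immunogenicity data, a set of topline tables will be generated". SAP 4.5.5 adds one condition and names who is unblinded: "The SAP was finalized prior to unblinding of individual participants for the pharmaceutical partner and PI".

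On late data, SAP 5.2 foresees that "Additional exploratory endpoint data not available at the time of CSR" preparation may be reported afterwards, in addenda or manuscripts. SAP 4.6.2 and 7.2 leave the remaining exploratory assays to a later SAP addendum.

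On masking of laboratories, Protocol 6.3.3 has one sentence: "Laboratory personnel performing immunological assays will receive serum blinded to participant ID number, specimen visit number, and allocation group". A broader sentence in the same section covers the trial team: "Participants, site investigators, and study personnel performing any study-related assessments following study product administration are blinded to product received".

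On who runs the assays, SAP 4.6.2 states that "sIgA titers and total sIgA concentrations, as measured by ELISA, will be reported by the laboratory at FluGen, Inc". It assigns BAMA to a university research laboratory and the plasma assays to a separate outside laboratory. Protocol 6.2.1 names the same company, FluGen, as supplier of the study vaccine.

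**The concern.** Reading an endpoint titre, accepting or rejecting a plate, and deciding on a repeat run all involve judgement. Masking keeps that judgement independent of treatment arm and visit. Under the plan as written, codes can be released to the vaccine's owner while one of its own laboratories still has samples to assay or re-assay. No provision keeps that laboratory masked for the late runs. If a late result were then questioned, the CSR could not show that it had been fixed before the arm was known.

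**Working it through.** No formula applies; the check is to set the passages side by side.

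**1. What has to happen before individual codes are opened**

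| Milestone | Source | What it gates |
|---|---|---|
| Lock of safety and baseline data | Protocol 9.4 | Participant-level unblinding |
| SAP final | SAP 4.5.5 | Unblinding of the partner and PI |
| Receipt of secondary assay data | Protocol 9.4, SAP 5.2 | Topline tables, not codes |
| Upload of assay data to the coordinating center's system | SAP 4.6.2 | Nothing stated |
| Freeze of any assay dataset | Neither document | Nothing stated |

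The first two rows are the only conditions on code release, and neither concerns assay data.

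**2. Which assays the laboratory sentence reaches**

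| Assay | Specimen | Tier at Day 29/57 | Laboratory (SAP 4.6.2) | Specimen named in 6.3.3? |
|---|---|---|---|---|
| HAI, MN | Serum | Secondary | University research laboratory | Yes |
| sIgA by BAMA | Nasal wash | Secondary | University research laboratory | No |
| HAI, MN, NAI | Plasma | Exploratory | Separate outside laboratory | No |
| sIgA by ELISA | Nasal wash | Exploratory | Manufacturer's laboratory | No |
| T-cell responses | Cells | Exploratory | Not stated | No |

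Only the ELISA row combines three features: a specimen outside the masking sentence, a laboratory belonging to the product's owner, and an owner named among those to be individually unblinded. The SAP describes no separation between the company's assay staff and its recipients of codes.

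**3. What was assayed before unblinding**

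SAP 5.6.1 says the interim analysis used serum, plasma and nasal-wash samples through Day 29 (Cohorts 1 to 3) and Day 57 (Cohort 4). It was run while the study was ongoing, where results were available, and participant-level immunogenicity data were withheld. Those results therefore came before the codes were opened.

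Two limits apply. Availability was not guaranteed. SAP 5.2 also dates the interim to the point when everyone had reached 28 days after the first vaccination, whereas Cohort 4's endpoint visit is 57 − 29 = 28 days later than that. SAP 2.1 records two addendums to the interim report, which may have filled the gap, but the documents do not say so.

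**4. What is left**

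- Post-IIV4 (Visit 6) samples, which were outside the interim; SAP Tables 13 to 22 all report this time point.
- Day 29 and Day 57 results missing at the interim.
- Repeat runs.
- Exploratory assays still to come.

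**5. Sensitivity of a summary to one call**

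Planned arms in Cohorts 1 to 4 have 10, 15 or 30 children (Protocol Table 2). If every child contributes, one changed call on a fold-rise threshold moves that arm's percentage by 1/10 = 10 points, 1/15 = 6.7 points or 1/30 = 3.3 points. This shows leverage only; it is not an estimate of bias, for which the documents give no basis.

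**The case against.** The strongest reply has five parts.

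- **The unblinding clause is a bound.** It sits in the paragraph on the interim analysis and reassures the reader that the interim will not unblind anyone. It does not direct that codes be opened at lock. That is right, and no passage dates the actual unblinding. But neither document supplies a later condition tied to assay data.
- **Other masking exists.** The general sentence in 6.3.3 blinds staff who perform study assessments, and Protocol 10.1.3 sends specimens out under coded numbers. This is partial cover. Neither provision names outside laboratories, masks the visit or says what holds after unblinding. A coded number can be matched to an arm once the organisation holds assignments under the same numbering. The word serum may be loose drafting, but the sentence should then say what it means.
- **Most Day 29/57 work came first.** This stands wherever interim data were available, and it shrinks the exposure to the residue in step 4.
- **The manufacturer's assay is exploratory and the analyses are descriptive (SAP 5.8).** This stands and lowers the stakes.
- **Specimen procedures are deferred to the Manual of Procedures.** It may contain laboratory firewalls, and it was not available for this review.

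Two stronger readings are tempting. A reader might count every nasal-wash and plasma endpoint in Protocol Section 3 (19 to 22 and 31 to 54) as exposed, and infer that the double blind does not extend to the mucosal endpoints. The documents do not support this: those endpoints are set at Day 1 and Day 29 or 57, the visits the interim covered, and the secondary mucosal assay is not run by the manufacturer. A reader might also infer that the manufacturer's assay staff hold individual codes or tested samples unblinded. No passage says either.

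**Conclusion.** The gap in the plan is real, and narrower than the unblinding clause alone suggests. Code release depends on clinical lock and a final SAP, while no assay dataset has to be received or frozen. The residual exposure is greatest for late runs of the manufacturer's nasal-wash ELISA. For BAMA and the plasma assays, the fault is missing masking wording and the absence of a freeze condition, without the added conflict of roles.

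The conclusion assumes that the Manual of Procedures does not already close the gap and that some assay work remained, or could be repeated, after codes were opened. There is no evidence that unblinded testing happened, and the size of any bias cannot be derived. The low cost of the remedy justifies the change.

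**What to change.** 1. In Protocol 9.4 and SAP 4.5.5, make participant-level unblinding conditional on clinical lock and on receipt and freeze of the secondary assay data.
2. For any assay completed later, withhold participant-level codes from the performing laboratory and its parent organisation until that dataset has been transferred and frozen. Name the manufacturer explicitly for the ELISA.
3. Extend the laboratory sentence in Protocol 6.3.3 to serum, plasma, nasal wash and cells, and to all laboratories.
4. In the CSR, state for each assay whether results were frozen before unblinding.

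The cost is a change of wording and a defined order for releasing codes; the manufacturer may receive individual assignments somewhat later. The documents do not show whether codes have already been released. If they have, item 4 is the only part still possible.
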